3.1.1 Dose Interruption and Reduction

It is recognized that some AEs may require dose adjustment or study drug discontinuation. Intra-subject dose reduction or escalation is permitted and based upon treatment-related adverse events observed ([Table 1](#)).

After experiencing an AE, subjects whose laboratory results return to baseline values and remain stable for 4 consecutive weeks have the option to increase the dose of SKI-O-703 1 dose level up to the randomized dose level.

Table 1 Guidelines for Dose Interruption or Reduction^a

AE	Occurrence	Action
ALT elevations (range 3 to 5 \times ULN) Alkaline Phosphatase > 3 \times ULN and > 2 \times baseline	First	
 If asymptomatic (no nausea, anorexia, vomiting), repeat test within 72 hours^b and, if stable or lower, may continue dosing of study drug. If on repeat test value has increased further but remains < 5 \times ULN and asymptomatic, withhold study drug and retest weekly until values becomes stable. When stabilized to < 5 \times ULN, continue dosing with the study drug. If symptomatic or > 5 \times ULN, withhold study drug. Follow the subject weekly until symptoms abate and values return to baseline per confirmation from central laboratory; at which time study drug may be restarted at a 50% reduced dose by taking only one daily dose. 
Note: Discontinue study drug permanently if the ALT elevation is accompanied by an elevation in direct bilirubin to > 2 mg/dL (34.2 mmol/L).

	Second	Discontinue study drug permanently.
ANC <1,000/mm ³ or febrile neutropenia	First	Withhold dose until ANC \geq 1000/mm ³ , or has returned to baseline, then reduce the dose by skipping one of the daily dose and increase to previous dose if ANC remains stable for 2 weeks on reduced dose.
	Second	Discontinue study drug permanently if the intolerance reoccurs or persists.
Sustained increased systolic (> 160 mmHg) or sustained increased diastolic (> 100 mmHg) blood pressure in a previously normotensive subject	First	
Study drug may be withheld for 5 to 7 days and then restarted at a reduced dose by skipping one of the daily dose.
 
Irrespective of study drug dose adjustment, subjects who develop a sustained increased systolic (>140 mmHg) or a sustained increased diastolic (>90 mmHg) blood pressure should be started on antihypertensive medications (e.g. lisinopril 5mg daily) or have their antihypertensive regimen adjusted if already on any antihypertensive agent.

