	Second	Discontinue study drug permanently if the hypertension reoccurs or persists.
Intolerable nausea or vomiting (see Section 5.8.2 for further details)	First	Study drug may be withheld for 5-7 days and then restarted at a reduced dose by skipping evening dose.
	Second	Discontinue study drug permanently if the intolerance reoccurs or persist.

AE	Occurrence	Action
QTcF >500 ms for female subject OR >480 ms for male subject, at any time point	-	
The ECG should be repeated as triplicate (all three within 2 minutes) and a cardiology consult may be obtained as medically necessary.
 
 • If the repeat ECG confirms QTcF >500 ms (females) or >480 ms (males), dosing must be interrupted for up to 14 days • If the QTcF resolves to ≤480 ms (males and females)/they may resume dosing at the reduced dose by skipping one of the doses (ie, morning or evening) • If the QTcF remains >480 ms (males and females) after 14 days of dose interruption, the study drug must be permanently discontinued.
QTcF change of >30 ms from baseline	-	If the QTcF has increased >30 ms when compared to the baseline with no other known etiology, and the principal investigator considers it clinically significant then a confirmatory ECG (single) will be performed and dose should be reduced by skipping one of the doses (ie, morning or evening) for the remainder of the study.

Abbreviations: ACE, angiotensin-converting-enzyme; AE, adverse event; ALT, alanine aminotransferase; ANC, absolute neutrophil count; AST, aspartate aminotransferase; ECG, electrocardiogram; LFTs, liver function tests; MOA, mechanism of action; QTcF, corrected QT interval by Fridericia formula; ULN, upper limit of normal

- a These are examples based on previously observed AEs for agents with similar MOA (ie, fostamatinib). All other potential/spontaneous Grade 3/4 AEs that can warrant dose reduction or interruption are not excluded and will be assessed on an ongoing basis during the study. Those would be evaluated upon judgment by the principal investigator and the safety operations team.
- b A central laboratory must be used for repeat ALT, AST, ALP, or ANC.

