7.4 Sample Size Calculations

A minimum of 60 subjects will be enrolled in the study. Subjects will receive either 200 mg BID or 400 mg BID of SKI-O-703 or placebo in a 2:2:1 ratio.

Based on [Podolanczuk et al \(2009\)](#) at least 50% of subjects in the active treatment group will be responders (R). A sample size of 24 subjects per active treatment group and 12 subjects in the placebo group will provide approximately 82.7% power to detect a difference between response rates of 50% and 1% in the active treatment and placebo groups, respectively, at the 2-sided 5% significance level. The test statistic used in the sample size calculation was the 2-sided Fisher's Exact test using the normal approximation method.

Subjects that do not receive the study drug or do not provide at least 1 post baseline measurement will be excluded from the analysis above and replaced.

There will be no adjustment for multiple comparisons. The sample size calculation was performed using PASS 15 Power Analysis and Sample Size Software (2017). NCSS, LLC. Kaysville, Utah, USA, ncss.com/software/pass.

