7.7.3 Analysis of Platelet Response

The primary efficacy endpoint will be summarized as overall platelet response rate (ORR) by treatment group and analyzed using Fisher's exact test to compare the difference in ORR between each active treatment group and placebo. A logistic regression model will also be performed on platelet response and include treatment, baseline platelet count and prior TPO-receptor agonist use, provided there are enough subjects in each subgroup. The odds ratio for the treatment effect compared to placebo (together with 95% CI and p-value) will be provided.

Summary statistics will be provided on the number (%) of subjects achieving platelet response by each treatment group and the combined active treatment group. Fisher's exact test on the differences in the ORR will therefore be provided for:

- Each active treatment group (200 mg BID, 400 mg BID) vs. placebo
- Combine active treatment groups vs. placebo
- 200 mg BID vs. 400 mg BID.

Furthermore, summary statistics will be provided on the number (%) of subjects achieving platelet response by each treatment group and the subgroups defined in [Section 7.6](#).

A subject will be classified as a platelet responder if subject shows at least 1 platelet count $\geq 30,000/\mu\text{L}$ and doubling the baseline (average of 2 previous counts), at any visit during treatment period, without use of rescue medication. The ITT analysis set will be used in the analysis of the primary endpoint.

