#### **4.3. Analysis Visit Window**

No analysis visit window is assigned. All data are summarized based on the visit name collected on the CRF page.

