## 8. Efficacy Analysis

The results for each efficacy endpoint will be summarized by treatment for all patients within the ITT set using descriptive statistical methods, and repeated within the PP set. Continuous variables (quantitative endpoints) will be summarized using the mean, the standard deviation (SD), median, range (minimum value and maximum value), and interquartile. Categorical variables (qualitative endpoints) will be summarized using frequency counts (number) and percentages. Data will be listed in data listings.

All statistical tests will be 2-sided using a 5% significance levels, leading to 95% (2-sided) confidence intervals (CIs). This will be used for each pairwise comparison with placebo, ie, there will be no adjustments for multiplicity since this is a Phase 2 study, and interim analysis will only be performed on safety and PK analysis.

If there are multiple post-baseline platelet count results in the same visit, the result from central lab will be used first. If there are more than one central lab result in the same visit, the result with larger platelet count will be used. However, if only local lab results exist, the local lab result with larger platelet count will be used.

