#### *Sensitivity analysis based on treatment-policy strategy:*

The primary analysis will be repeated on assessments in all scheduled visits from post-baseline until Week 12, regardless of patients using rescue medication or discontinuation. The missing platelet count values will be imputed by Multiple Imputation (MI) method for all treatment groups, under the missing at random (MAR) framework.

The SAS procedure MI will be used to impute missing platelet count at the scheduled analysis visits (up to Week 12) to create 25 complete data sets. The missing data patterns

will be checked by treatment and at the scheduled visits for the platelet count. If there are non-monotone missing patterns, two separate imputation procedures will be used to complete the imputation process.

In the first step, the Markov Chain Monte Carlo (MCMC) method will be used to impute missing values by treatment to create 25 imputed data sets with monotone missing patterns. The seed will be set to 7032101, the imputed values will be rounded to 3 decimals with  $10^9/L$  unit and a single chain will be used to produce imputations.

In the second step, the monotone regression method will be used to impute the remaining missing values for the 25 data sets with monotone missing patterns. The MONOTONE REG statement will be used with seed 2101703. The missing values at each visit will be imputed based on treatment, values at baseline and previous visits, and prior TPO-receptor agonist use.

If model fail to converge because the number of visits is more than number of subjects, the model will be reformed. The nearest visits (Week 1 Day 1 to Week 2 Day 8, Week 3 to Week 7, and Week 9 to Week 12) will be imputed by two steps imputation procedures described above separately with unique seed. For visits Week 1 Day 1 to Week 2 Day 8, the seed used in first step is 7032101 and in second step is 2101703. For visits Week 3 to Week 7, the seed used in first step is 1021984 and in second step is 1984102. For visits Week 9 to Week 12, the seed used in first step is 1072018 and in second step is 2018107.

After the completion of two steps imputations, the response will be defined based on platelet counts in the 25 complete datasets and the same logistic regression model described in [Section 8.1.1](#) will be used to analyze the 25 complete datasets. The SAS procedure MIANALYZE will be used to combine the results for the statistical inferences.

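### The plan does not fix which platelet counts qualify for response, and SAP section 8 resolves same-visit repeats by keeping the larger count

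*SAP*

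**What the plan says.** Protocol 7.7.3 classes a subject as a responder on a single count that reaches 30,000/µL and twice baseline, "at any visit during treatment period, without use of rescue medication". Protocol 7.1 and SAP 3.2.1 and 8.1 also use any visit. None of them limits the set to scheduled visits.

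SAP 4.3 assigns no analysis windows: "All data are summarized based on the visit name collected on the CRF page". SAP 8 puts central results ahead of local ones within a visit, and then: "If there are more than one central lab result in the same visit, the result with larger platelet count will be used". The same larger-value rule applies when only local results exist. For other laboratory parameters SAP 9.3 takes the worst value, and it sends platelets back to the section 8 rule.

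The Schedule of Events (Protocol Table 2) has eight post-dose on-treatment hematology draws: Day 4, Day 8 and Weeks 3, 5, 7, 9, 11 and 12. It also marks hematology in the Early Withdrawal/Unscheduled column. Protocol 6.4.4 includes the platelet count in hematology.

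For platelet efficacy, a scheduled-visit set is named only for the multiple-imputation sensitivity analyses. SAP 8.1.2 uses "assessments in all scheduled visits from post-baseline until Week 12", but that analysis also disregards rescue use and imputes missing counts.

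**The concern.** There are two separate problems.

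The first is explicit. When a visit has several results from the same type of laboratory, the analysed value depends on the outcome itself. Keeping the larger count can raise responder status, the two-count endpoints, peak count and change from baseline, and cannot lower them.

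The second arises from silence. Platelet counts fluctuate, so with a one-count endpoint every further eligible count is another chance to cross the threshold. Protocol Table 1 sends patients with certain laboratory events back for repeat testing. One instruction is to "withhold study drug and retest weekly until values becomes stable", and a footnote adds: "A central laboratory must be used for repeat ALT, AST, ALP, or ANC". Another footnote says the listed events were seen with agents of similar mechanism, and Protocol 1.5 lists liver enzyme changes as a potential risk of this drug. Extra counts could therefore plausibly gather in the active arms, and blinding would not prevent that because retesting follows toxicity. At stake is an overstated response rate, and possibly an overstated difference from a placebo group of 12, in a trial meant to guide further development.

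**Working it through.** **The plan's own figure.** Inputs from Protocol 7.4 are 24 versus 12 patients, 50% versus 1%, and a two-sided 5% level. Using the normal approximation with continuity correction:

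- pooled rate = (24×0.50 + 12×0.01)/36 = 0.3367
- SE under the null = √[0.3367×0.6633×(1/24+1/12)] = 0.1671
- SE under the alternative = √[0.25/24 + 0.0099/12] = 0.1060
- correction = ½(1/24+1/12) = 0.0625
- power = Φ[(0.49 − 0.0625 − 1.96×0.1671)/0.1060] = Φ(0.943) = 82.7%

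This matches the stated 82.7% (82.74% in the SAP). Full enumeration of Fisher's exact test gives 93.9%. Neither calculation uses the number of visits, so the point below does not change the stated power.

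**Extra looks, closed form.** Let P be the chance-response probability over the 8 scheduled counts, with independent counts. The per-count probability is q = 1 − (1−P)^(1/8), and with k extra counts the probability becomes 1 − (1−q)^(8+k). P is assumed.

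| P over 8 counts | 1 extra | 2 extra | 4 extra |
|---|---|---|---|
| 1% | 1.1% | 1.2% | 1.5% |
| 5% | 5.6% | 6.2% | 7.4% |
| 10% | 11.2% | 12.3% | 14.6% |
| 20% | 22.2% | 24.3% | 28.5% |

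Keeping the larger of two independent results at one visit is equivalent to one extra count, so the column for 1 extra also sizes the section 8 rule for one repeat.

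**Extra looks, simulated.** The assumptions are no drug effect, between-patient log-SD 0.4 around 15,000/µL, two baseline counts both below 30,000/µL, and response at 30,000/µL or more and at least double their mean. The documents give no within-patient variability.

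| Within-patient log-SD | 8 counts | 12 counts | 14 counts |
|---|---|---|---|
| 0.2 | 0.5% | 0.8% | 0.9% |
| 0.3 | 6.9% | 9.6% | 10.8% |
| 0.4 | 19.2% | 25.3% | 27.8% |

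At log-SD 0.3 to 0.4 the gain per retested patient runs from 9.6 − 6.9 = 2.7 points (4 extra counts) to 27.8 − 19.2 = 8.6 points (6 extra). With the lowest-count baseline of SAP 4.2 the levels are higher: 11.6%, 15.2% and 16.7% at 0.3, and 24.7%, 31.5% and 34.2% at 0.4. With serially correlated counts (assumed decay time 14 to 28 days) the gain falls to about 0.5 to 4 points.

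**Arm level.** Multiply by the assumed share of active patients retested. The range is 0.10×2.7 = 0.3 points to 0.50×8.6 = 4.3 points, or about 0.1 to 1 patient in 24. The planned difference is 49 points.

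**Test error.** The SAP states: "All statistical tests will be 2-sided using a 5% significance levels". Fisher's test was enumerated at 24 versus 12 with no drug effect and 4 extra counts per retested active patient. Each cell gives the two-sided total, with the part favouring active in brackets.

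| Chance response | No extra counts | Half of active retested | All of active retested |
|---|---|---|---|
| 10% | 1.6% (0.05%) | 1.1% (0.18%) | 1.1% (0.49%) |
| 20% | 2.5% (0.7%) | 2.6% (1.8%) | 4.1% (3.8%) |

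At the planned 1% placebo rate the error is practically zero.

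**The case against.** A reader might infer that the plan demonstrably biases the comparison towards the drug. The documents do not support that, for five reasons.

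- No passage says that unscheduled counts qualify. Their inclusion follows from any visit plus silence. Elsewhere the SAP mentions unscheduled data when it means them: the laboratory listings in 9.3 and the vital-sign baseline in 9.4. The worked example in 8.1.1 uses scheduled visit names.
- The larger-count rule acts within one visit and one laboratory type. A retest recorded under its own visit name never meets it, and a central result displaces a local one even when it is lower.
- ALT and ALP retests are chemistry. They yield a platelet count only if hematology is drawn too. Of the Table 1 laboratory triggers, only the neutrophil retest necessarily brings a blood count.
- The direction is not established. The healthy-volunteer studies in Protocol 1.1 showed no laboratory signal. Weekly enzyme retests occur while drug is withheld, second events lead to discontinuation, and early bleeding could bring placebo patients in for extra visits.
- The two-sided error of Fisher's test did not exceed 5% in any scenario tried.

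There are also partial safeguards. Several secondary endpoints need two consecutive counts at least 5 days apart, and one sensitivity analysis uses scheduled visits.

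All of this stands against the strong reading. It does not answer the narrower point. The repeat rule is explicit and outcome-dependent, the qualifying visit set is unspecified, and no planned analysis isolates either. SAP 8.1 also has a sentence about averaging the last two counts, which could soften the one-count premise but conflicts with Protocol 7.7.3. Even under averaging, 4 extra counts raised false response from about 6% to 8% in a second assumed population (within-patient CV 30%, lowest-count baseline), against about 15% to 20% with a single count.

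**Conclusion.** The point holds in a limited form. The rule that keeps the larger same-visit repeat selects on the outcome and should go. The visit set for the primary endpoint should be stated, because a one-count endpoint is sensitive to how many counts are eligible.

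The size is modest: about 3 to 9 points of false-response probability for a patient with 4 to 6 extra counts, and roughly 0.3 to 4 points for an arm. These figures rest on assumed log-SDs of 0.3 to 0.4, independent counts, retesting in 10% to 50% of active patients with none on placebo, and admission of unscheduled counts. They shrink with serial correlation and are negligible at log-SD 0.2. A net bias towards the active arms is possible but not shown. The concern is inflated response rates and differences, not a test that exceeds its nominal error.

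**What to change.** - **SAP 8:** replace the larger-count rule with one that does not depend on the value. Take the central result closest to the planned day, the first if tied, and apply the same rule when only local results exist.
- **Protocol 7.1 and 7.7.3, SAP 8.1 and 8.1.1:** base responder status and the other count endpoints on the scheduled post-dose visits from Day 4 to Week 12. Use an unscheduled or on-treatment early-withdrawal count only to fill a missing scheduled count within that visit's window in the Schedule of Events.
- **Sensitivity and reporting:** keep the any-count version as a sensitivity analysis, and report the number of platelet counts per patient by arm so that any imbalance is visible.
- **Reconcile** the sentence in SAP 8.1 on averaging the last two counts with the single-count rule in Protocol 7.7.3.

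The cost is wording and programming, with no new data collection. The downside is that a true response seen only at an unscheduled visit would not count in the main analysis, and response rates may be slightly lower. The any-count sensitivity analysis would show how much this matters.

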### 8.1. Primary Efficacy Endpoint

The primary efficacy endpoint, patient platelet response, is defined as platelet count  $\geq$  30,000/ $\mu$ L and doubling the baseline (average of 2 previous counts), at any visit during the treatment period and without a use of rescue medication. Refer baseline definition to Section 4.2. The average based on last 2 platelet counts at the time of evaluation.

#### 8.1.1. Primary Analysis

The platelet responses after using rescue medication during treatment period will be set to missing and will be imputed as the average of the last 2 previous non-missing platelet counts. For example, if platelet count in Week 2 Day 8, Week 3 and Week 5 are 45,000, missing, and 48,000 respectively, the average will be calculated by results from Week 2 Day 8 and Week 5.

The primary efficacy endpoint will be summarized as overall platelet response rate (ORR) with exact unconditional 95% confidence intervals (CI) by treatment group. The ORR difference and exact unconditional 95% CI will be provided between each of active treatment groups and placebo group, and between two active treatment groups. The p-value from Fisher's exact test will be presented.

For patients whose ORR cannot be adequately determined, their ORR will be imputed using a non-responder imputation (NRI) approach.

Summary statistics will be provided on the number (%) of patients achieving platelet response by each treatment and the combined active treatment groups. The differences in the ORR, 95% CI and p-value from a Fisher's exact test will therefore be provided for:

- Each active treatment group (200 mg BID, 400 mg BID) vs. placebo
- Combine active treatment groups vs. placebo
- 200 mg BID vs. 400 mg BID.

A logistic regression model will also be performed on platelet response as dependent variable and treatment group, baseline platelet count and prior TPO-receptor agonist use as covariates. The odds ratio for the treatment effect compared to placebo (together with 95% CI and p-value) will be provided.

Bar plots on difference in proportions of ORR and exact unconditional 95% CI will be provided by treatment group and combined active treatment group.

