5.8 Prior and Concomitant Therapy

Use of all concomitant medications that the subject is receiving at the time of Screening or receives during the study must be recorded in the subject's eCRF. The minimum requirement is the reason for drug use, drug name, and the dates of administration (including start and end dates), dosage information including dose, route, and frequency are to be recorded in the eCRF. This will include all prescription drugs, herbal products, vitamins, minerals, vaccines, and over-the-counter medications (including folic acid). Any changes in concomitant medications also will be recorded in the subject's eCRF.

Any concomitant medication, except the prohibited medications listed in [Section 5.8.3](#), deemed necessary for the welfare of the subject during the study may be given at the discretion of the investigator. However, it is the responsibility of the investigator to ensure that details regarding the medication are recorded in full in the eCRF.

Subjects will be allowed to receive stable doses of background medications in line with the current standard of care. The background medications allowed include corticosteroids (<20 mg prednisone equivalent per day) and immunosuppressive drugs such as azathioprine (≤ 50 mg twice daily), mycophenolate mofetil (≤ 500 mg twice daily), and cyclosporine (≤ 100 mg twice daily). The dose of such background medications should be fixed for at least 2 weeks before Day 1 and remain unchanged until 12 weeks of treatment have been completed or unless rescue therapy is required.

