5.8.3 Prohibited Concomitant Medications

The medical monitor must be notified in advance (or as soon as possible thereafter) of any instances in which prohibited medications are administered. Prohibited medications during the study include:

- Any biological agents for the treatment of ITP
- Any rescue medications other than those described in [Section 5.8.1](#)
- Any immunosuppressant drugs other than those described in [Section 5.8](#)
- Change in corticosteroid and immunosuppressants dose as detailed in the exclusion criteria

- Use of IVIGs within 4 weeks prior to Day 1
- Treatment with rituximab or splenectomy within the 8 weeks prior to Day 1
- Any parenteral antibiotics as specified in the exclusion criteria
- Any live vaccine taken within 28 days prior to Day 1 or plan to receive one during the study
- Concomitant use of any anticoagulants and platelet aggregation inhibiting drugs including aspirin (within 14 days of planned dosing through end of follow-up)
- Known CYP1A2 and UGT1A1 inhibitors and inducers (See [Appendix 13.1](#) for a list of suggested named CYP1A2 and UGT1A1 inhibitors and inducers). These medications must be discontinued within 5 half-lives or 4 weeks prior to Day 1, whichever is longer.

6 Study Assessments and Procedures

Before performing any study procedures, all potential subjects will sign an ICF. Subjects will have the opportunity to have any questions answered before signing the ICF. The investigator must address all questions raised by the subject. The investigator will also sign the ICF.

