7.1 Primary Endpoint - Platelet Response

- Patient platelet response is defined as platelet count $\geq 30,000/\mu\text{L}$ and doubling the baseline (average of 2 previous counts), at any visit during the treatment period and without the use of rescue medication

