##### **4.6.3. Per-protocol (PP) set**

The PP set will consist of all patients in ITT set with no major protocol violations that may impact the analysis. Major protocol violations will be identified during the study according to the protocol deviation list and treatment compliance defined in [Section 7.4.2](#). Patients will be analyzed according to the treatment arm to which they were randomized. This analysis set will be used for efficacy summaries, including the analysis of the primary endpoint.

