## 7. Treatments and Medications

### 7.1. Prior and Concomitant Medications

Use of all concomitant medications that the patient is receiving at the time of Screening or receives during the study must be recorded in the patient's eCRF. All medications will be coded according to the World Health Organization Drug Dictionary (WHODD) Enhanced B3 March 2018 or later.

A prior medication is defined as any medication that has a stop date prior to the first dose of study drug (SKI-O-703 or placebo). Concomitant medications are defined as medications that are started between the first dose of study drug (SKI-O-703 or placebo) date and the last dose of study drug (SKI-O-703 or placebo) date, both inclusive, or started before the first dose of study drug (SKI-O-703 or placebo) date but ended or remain ongoing while on treatment. Incomplete medication start and stop dates will be imputed as per [Section 4.7](#).

The frequency table will be provided by treatment group and overall on ITT set. The number and percentages of patients who had any prior medications will be summarized overall and by treatment groups, therapeutic drug classes (ATC level 2) and generic drug names. Therapeutic drug classes and generic drug names will be presented in a descending order of overall patient frequency, then the patient frequency within treatment groups from high dose to low dose and placebo group, if applicable. Similar frequency tables will be provided for permitted concomitant medications and prohibited concomitant medications on ITT set. The prohibited concomitant medications are defined in protocol Section 5.8.3.

The list of prohibited concomitant medications should be reviewed and finalized by sponsor designee before final database lock.

A listing of prior and concomitant medications by patient will be provided, with an indicator to identify the prior and concomitant medications.

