## 7.2. Rescue Medications

In case of bleeding events requiring rescue medication, the following rescue medications are permitted: IVIG 1 g/kg/day for 2 days (ie, 2 g/kg), romiplostim 2 to 5 µg/kg, dexamethasone 40 mg/day for 4 days, other high dose parenteral steroids (ie, solumedrol 1 g IV), platelet transfusions (these may be reserved for serious or life threatening bleeding events), or standard of care as per participating countries. Patients should be withdrawn in case of CNS bleeding or life-threatening GI bleeding (see protocol Section 4.2.1).

Rescue medications will be coded to therapeutic drug classes (ATC level 2) and generic drug names using WHODD Enhanced B3 March 2018 or later. The number and percentages of patients who had any rescue medications will be summarized overall and by treatment, therapeutic drug classes (ATC level 2) and generic drug names based on ITT set. Therapeutic drug classes and generic drug names will be presented in a descending order of overall patient frequency, then the patient frequency within treatment groups from high dose to low dose and placebo group, if applicable.

A listing with all rescue medications will be generated.

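### Only counts after rescue medication are set aside in the primary analysis, so a count raised by prohibited or otherwise unlabelled ITP therapy can score as a platelet response

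*SAP*

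**What the plan says.** **Endpoint.** A responder needs one count of at least 30,000/µL that also doubles baseline, "at any visit during the treatment period and without the use of rescue medication" (Protocol 7.1; SAP 3.2.1 and 8.1 agree). The endpoint wording has no bleeding condition.

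**Handling in the analysis.** SAP 8.1.1: "The platelet responses after using rescue medication during treatment period will be set to missing". The values set aside are then imputed. No other therapy triggers this step.

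**What rescue is.** SAP 7.2 and Protocol 5.8.1 open with the same words: "In case of bleeding events requiring rescue medication, the following rescue medications are permitted". The list that follows ends with local standard of care, so it is not closed.

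**Other ITP therapy.** Protocol 5.8 fixes background steroid and immunosuppressant doses through Week 12 unless rescue is needed. Apart from prohibited drugs, it says that a medication "deemed necessary for the welfare of the subject during the study may be given at the discretion of the investigator". Protocol 5.8.3 prohibits, among others, biological agents for ITP, other immunosuppressants, and "Any rescue medications other than those described in" Section 5.8.1.

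**What the SAP does with prohibited drugs.** SAP 7.1: "Similar frequency tables will be provided for permitted concomitant medications and prohibited concomitant medications on ITT set". It adds: "The list of prohibited concomitant medications should be reviewed and finalized by sponsor designee before final database lock". Nothing connects that list to the derivation of response.

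**Per-protocol set.** SAP 4.6.3 keeps ITT patients with "no major protocol violations that may impact the analysis", and SAP 8 repeats the efficacy summaries in this set.

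**The concern.** Patients enter with counts below 30,000/µL, one randomization stratum is below 15,000/µL, and one patient in five is assigned placebo for 12 weeks. An investigator may start or increase ITP therapy because of a low count before any bleed. There are eight scheduled post-baseline counts on treatment (Day 4, Day 8, Weeks 3, 5, 7, 9, 11 and 12), and one qualifying count is enough, so a short-lived rise from another drug can make a responder.

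For such a patient the primary outcome depends on whether the drug was recorded as rescue. If it was, later counts are set aside. If it was recorded as a prohibited or other medication, they stand, and an effect of another ITP therapy is credited to study drug or placebo.

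**Working it through.** **Step 1. Follow the patient through the plan.** Take a patient with no response so far who starts or increases ITP therapy without a bleed and then has a qualifying count.

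| Provision | Effect on that count |
|---|---|
| SAP 8.1.1, drug recorded as rescue | Set aside |
| SAP 8.1.1, drug recorded as prohibited or otherwise not rescue | Kept; scores as a response |
| SAP 7.1 | Prohibited drug appears in a table and listing only |
| SAP 4.6.2, ITT set | Patient stays in |
| SAP 4.6.3, per-protocol set | Patient may be dropped as a major violator; response is not rescored |
| SAP 8.1.1, non-responder imputation | Covers response that cannot be determined; here a count exists |
| SAP 8.1.2, 28-day window | Acts on rescue only |
| SAP 8.1.2, treatment policy | Keeps all counts by design |

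No row removes a count after unlabelled ITP therapy while keeping the patient in the analysis.

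**Step 2. Reproduce the plan's figure.** Inputs (Protocol 7.4, SAP 4.4): 24 active, 12 placebo, rates 50% and 1%, two-sided 5%. A pooled-variance normal approximation with continuity correction uses:

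- Pooled rate = (12×0.01 + 24×0.50)/36 = 0.3367
- SE under the null = √[0.3367×0.6633×(1/12 + 1/24)] = 0.1671
- SE under the alternative = √(0.01×0.99/12 + 0.50×0.50/24) = 0.1060
- Correction = 0.5×(1/12 + 1/24) = 0.0625
- Power = Φ[(0.49 − 0.0625 − 1.96×0.1671)/0.1060] = Φ(0.943) = 82.7%

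This matches the stated 82.7% (82.74% in the SAP). Full enumeration of Fisher's exact test at the same inputs gives 93.9%. The illustrations below use enumeration, so they should be compared with 93.9%.

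**Step 3. Weight of one patient.** Placebo: 1/12 = 8.3 percentage points. One active dose: 1/24 = 4.2 points.

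**Step 4. Fisher's exact p, two-sided, by number of placebo responders.** Each p sums the hypergeometric probabilities no larger than that of the observed table. For 12/24 against 0/12, the observed table has probability C(24,12)/C(36,12) = 2,704,156/1,251,677,700 = 0.00216; adding the smaller terms in the other tail gives 0.0025.

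| Active responders | 0/12 | 1/12 | 2/12 |
|---|---|---|---|
| 9/24 | 0.016 | 0.115 | 0.268 |
| 10/24 | 0.015 | 0.059 | 0.260 |
| 12/24 (planned rate) | 0.0025 | 0.025 | 0.076 |
| 13/24 | 0.0022 | 0.011 | 0.040 |
| 24/48 (doses combined) | 0.0018 | 0.0096 | 0.052 |

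At the planned rate, one false placebo responder leaves significance and two remove it. At 9/24 or 10/24, one is enough; at 13/24, two are not.

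**Step 5. Power under assumed rates.** The documents give no rate for this event. Assume that each true non-responder has probability q of being mis-scored as a responder, so that a rate p becomes p + (1 − p)q. Exact power:

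| q | Active / placebo rate | Both arms affected | Placebo only |
|---|---|---|---|
| 0 | 50% / 1% | 93.9% | 93.9% |
| 2% | 51% / 3.0% | 89.3% | 87.9% |
| 5% | 52.5% / 6.0% | 83.2% | 78.4% |
| 10% | 55% / 10.9% | 73.7% | 62.2% |

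The placebo-only column holds the active rate at 50%. If only an active arm is affected, its rate is overstated by 1, 2.5 or 5 points at these values of q.

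**The case against.** **The ordinary-concomitant route is narrow.** A reader might infer from the discretion clause in Protocol 5.8 that any new ITP drug could be given freely and escape the rule. The documents do not support that. The clause excludes the drugs prohibited in 5.8.3, and the same section fixes background doses unless rescue is required. A raised background dose is therefore either rescue or a departure from the protocol. This objection stands. What remains through that route is ITP therapy that is neither prohibited nor recognised as rescue. It does not help with prohibited therapy, which the SAP tabulates without rescoring.

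**Rescue is not defined by a bleed.** A reader might also infer that treatment without a bleed can never be rescue. The text does not say so: it states what is permitted when a bleed needs rescue, the endpoint carries no bleeding condition, and 5.8.3 speaks of rescue beyond the list. Sites may well flag such therapy correctly, and the eCRF instructions are not in these documents. This also stands, but it shows that both readings are open. It does not supply a rule.

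**There are safeguards.** The medical monitor must be told of prohibited drugs, noncompliance can lead to withdrawal, and a gap between ITT and per-protocol results would be visible. None of these changes the ITT score.

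**The power figures rest on assumptions.** They would fit any misclassification of this size. At 5% in both arms, exact power is 83.2%, close to the stated 82.7%, although the methods differ. Mis-scoring confined to placebo works against the drug. All of this is fair, and the figures are illustrations only.

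**Conclusion.** The gap is real and is one of definition. As written, a count raised by prohibited or otherwise unlabelled new or increased ITP therapy can stay in the ITT primary analysis and score as a response, and no planned analysis rescores it. The conclusion rests on the text and does not need the power figures.

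Its size cannot be estimated from the documents. A reader might infer that the trial is biased toward the drug, or that power is materially reduced. Neither follows, because both the frequency and the arm are unknown: extra placebo responders hide an effect and extra active responders inflate it. What can be said is that with 12 placebo patients each case is worth 8.3 points and that, at 12/24 active, two false placebo responders move p from 0.0025 to 0.076.

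Priority lies between worth considering and should be fixed. The number of cases may be small, but the rule is cheap to settle before lock, and settling it after unblinding would be open to the charge of being data-driven.

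**What to change.** Before database lock, define rescue once, in SAP 7.2:

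*Rescue medication is any ITP-directed therapy newly started after the first dose of study drug, or any background ITP medication increased after that dose because of ITP, with or without a bleed and whether permitted or prohibited. It includes platelet transfusion and splenectomy.*

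- **Identification.** Find cases by blinded review, alongside the pre-lock review of prohibited medications in SAP 7.1.
- **Scope.** Use this definition everywhere the term appears: the primary endpoint and the other rescue-excluded endpoints, the rescue-use endpoint (SAP 3.2.2.4), the rescue covariate in the ANCOVA (SAP 8.2.2), and the 28-day and hypothetical-strategy analyses. Changing it only for the primary endpoint would give the word two meanings.
- **28-day rules.** Count from the last dose, treat an ongoing increased dose as continuing use, and treat every count after splenectomy as post-rescue. Otherwise a count on day 29 after splenectomy would score as a response.
- **Handling.** Treat later counts as SAP 8.1.1 already treats counts after rescue.

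**Cost.** The change needs a SAP revision in several sections and a somewhat wider blinded review. It needs no protocol amendment and no new data, because Protocol 5.8 already records each medication with reason, dose and dates, and procedures have their own eCRF pages (SAP 6.6). A few patients lose responder status, possibly including a true responder whose background dose was raised. Classification still relies on the recorded reason for use, so a count raised by steroids given for another illness would still score.
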